3.7.1.1 SUBGROUP ANALYSES FOR CO-PRIMARY ENDPOINTS

The two Co-primary endpoints will be summarized by the following demographic and baseline characteristics:

- Race (white, non-white).
- Ethnicity (Hispanic, non-Hispanic).
- Age (<65, ≥65).
- Sex (Male, Female).
- SOMA treatment area (≤ 500 cm², > 500 cm²).
- Overall TBSA (< Median, ≥Median)

3.7.2 Secondary Endpoint Analysis

The secondary endpoints of this study are:

 Incidence of confirmed complete wound closure of the Study Tx sites at Days 14, 21, 28, and 42, Month 2, and Month 3.

Confirmed complete wound closure will be assessed at Days 14, 21, 28, and 42, Month 2, and Month 3. The incidence will be calculated at the time point and covered the time period (table below):

Time Point	Time period covered	Denominator
Day 14	Day 14 to <day 21<="" td="">Subjects with Day 14 assessment	</day>	Subjects with Day 14 assessment
Day 21	Day 21 to <day 28<="" td="">Subjects with Day 21 assessment	</day>	Subjects with Day 21 assessment
Day 28	Day 28 to <day 42<="" td="">Subjects with Day 28 assessment	</day>	Subjects with Day 28 assessment
Day 42	Day 42 to <month 2<="" td="">Subjects with Day 42 assessment	</month>	Subjects with Day 42 assessment
Month 2	Month 2 to <month 3<="" td="">Subjects with Month 2 assessment	</month>	Subjects with Month 2 assessment
Month 3	Month 3 to <month 6<="" td="">Subjects with Month 3 assessment	</month>	Subjects with Month 3 assessment
Month 6	Month 6 to EOS	Subjects with Month 6 assessment

No P-value is to be provided for difference of percent of complete wound closure between treatment sites.

 Percent re-epithelialization of the Study Tx sites at Day 14, 21, 28, and 42, Month 2 and Month 3

The percent re-epithelialization values of both AG Tx and SOMA Tx at Day 14, 21, 28, and 42, Month 2 and Month 3 will be summarized with n, mean, standard deviation, median, minimum, and maximum. If the wound is closed, it is assumed to have 100% re-epithelialization.

The screened P-value is derived from paired t-test.

Percent subjects with durable wound closure of Study Tx sites at Months 3, 6, and 12

Durable wound closure is defined as persistence of closure, maintained for at least 3 months after the initial observation of closure.

The proportion and 95% confidence interval of subjects who have durable wound closure at Month 6 and Month 12 will also be presented. The proportion and 95% CI will be calculated using the exact method to the binomial distribution.

 Patient and Observer Scar Assessment Scale/Patient Scar Assessment Questionnaire (POSAS/PSAQ scores of Study Tx sites at Day 28, Months 2, 3, 6, and 12.

The POSAS/PSAQ scores will be summarized with number of subjects (n), Mean, Median, Standard deviation, Minimum, and Maximum at Day 28, Month 2, 3, 6, and 12 for AG Tx and SOMA Tx sites.

The screened P-values on total score of POSAS between treatment sites is derived from paired ttest.

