2. SCHEDULE OF ACTIVITIES

Table 1: Schedule of Activities

	Day -14 to Day -1	Day 1	Day 7± 1d	Day 14± 2d	Day 21 ± 2d	Day 28± 3d	Day 42± 4d	Month 2 ± 4d	Month 3 ± 7d	Month 6 ± 2Wks	Month 12± 4Wks
Assessments											
Informed consent ^a	√										
Physical examination and medical history review	√										
Laboratory tests (CMP and CBC with differential) ^b		√				√					
Pregnancy test (women of childbearing potential) ^b	√										
Blood samples for immunogenicity (PRA & anti-BSA) ^c		√							√		
Vital signs	√	√	√	√	√	√	√	√	√	√	√
Archival blood sample collection ^c		√									
Study Tx application		√									
Photograph Study Tx sites ^d		√	√	√	√	√	√	√	√	√	√
Study site surveillance ^e		√	√	√	√	√	√	√	√	√	√
Blinded wound assessments ^f			√	√	√	√	√	√	√	√	√
Concomitant medications		√	√	√	√	√	√	√	√	√	√
Concomitant procedures		√	√	√	√	√	√	√	√	√	√
Assessment and reporting of AEs	√	√	√	√	√	√	√	√	√	√	√

Assessments	Day -14 to Day -1	Day 1	Day 7± 1d	Day 14± 2d	Day 21 ± 2d	Day 28± 3d	Day 42± 4d	Month 2 ± 4d	Month 3 ± 7d	Month 6 ± 2Wks	Month 12± 4Wks
Quality of healed Study Tx sites (POSAS/PSAQ) ^g						√		√	√	√	√
Biopsy of healed SOMA Tx site and adjacent uninjured skin ^h								√			

^a Study Tx consent, including consent for photos, biopsy and for direct contact by sponsor post-study.

^b Processed by local laboratory. Obtain within 48 hours prior to application of StrataGraft.

^c Processed by central laboratory. Collected BEFORE StrataGraft placement.

^d Photos will be taken of the Study Tx sites prior to excision, following excision and hemostasis, and following placement of the Study Tx. During hospital stay, photos will be taken weekly. Following hospital discharge, the subject will have the option to submit photographs of the Study Tx sites each week until Month 3, every other week until Month 6, and then monthly until the Month 12 visit.

^e Study site surveillance includes assessment of local wound area for signs of infection, site adverse events, and graft loss.

^f Blinded assessor will assess all treatment sites for percent epithelialization beginning at Day 7 then and daily, or as often as possible, during dressing changes until complete closure is observed. A second observation of complete closure at least 2 weeks after the initial observation is required to confirm closure. Thereafter maintenance of closure will be assessed at each study visit, to assess durability of closure.

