5.5. Justification for Dose

A major factor limiting survival following extensive thermal injury is insufficient availability of healthy donor sites to provide enough skin for the required grafting procedures. In order to minimize the amount of donor site harvested, donor skin is often meshed to allow expansion of the autograft and increase the wound area that can be covered. However, such expansion carries risks such as infection of the wound bed within the interstices or long-term scarring of these open areas, resulting impairment of the graft to successfully incorporate and revascularize (ie, “take”) into the wound due to desiccation in the former or in a poor cosmetic and/or functional outcome in the case of the latter. Any such graft loss usually necessitates additional grafting and increases

the risks of morbidity and mortality. Alexander hypothesized that the application of allograft over widely meshed autograft would serve as a protective biological dressing as the autograft re-vascularized and then re-epithelialized the mesh interstices. They reported the successful use of cadaver skin as an overlay of widely meshed autograft in preventing these potential adverse outcomes in 14 subjects and 22 grafting procedures of 1% to 15% TBSA. However, although successful in gaining wound closure, it did not prevent scarring in the interstices due to the lack of a dermis in these areas (Alexander, 1981).

The use of Apligraf[®], a similar FT living-skin analog, was reported in 38 patients comparing outcomes to an inpatient control of split thickness skin graft alone meshed at the same ratio (Waymack, 2000). Under the Apligraf overlay, the median number of days to >75% closure of the interstices was 8 days compared to 13 days for the control sites. Of interest, wounds with Apligraf overlay of split thickness skin graft exhibited significant improvement in pliability compared to the autograft alone wounds with the former achieving normal pliability in a median of 35 days compared to such restoration in the autograft alone wounds in a median of more than 849 days. However, Apligraf has not been approved for this use.

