9.1. Efficacy Assessments

9.1.1. Wound Closure

Complete wound closure is defined as complete skin re-epithelialization without drainage confirmed at 2 visits at least 2 weeks apart but no later than Week 20. Complete wound closure will be considered to have occurred at the earlier of the two observations of complete skin re-epithelialization without drainage. The blinded assessor will evaluate treatment site(s) and assess the proportion of the treated wound closed beginning at Day 7 and then daily, or as often as possible, during dressing changes until wound closure is achieved.

Durable wound closure is defined as persistence of closure, maintained for at least 3 months after the initial observation of closure (FDA, 2006). The blinded assessor will evaluate the wound sites at each visit subsequent to wound closure to assess the maintenance of the closure.

Both complete wound closure and durable wound closure will be assessed by direct clinician observation during a study visit. Confirmation of closure (ie, the visit 2 weeks after the first observation of closure), may be assessed by direct clinical observation or by subject-provided photographs, per Schedule of Activities (Table 1).

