f Blinded assessor will assess all treatment sites for percent epithelialization beginning at Day 7 then and daily, or as often as possible, during dressing changes until complete closure is observed. A second observation of complete closure at least 2 weeks after the initial observation is required to confirm closure. Thereafter maintenance of closure will be assessed at each study visit, to assess durability of closure.

g All POSAS Observer assessments will be performed by blinded assessor, first at the time of closure, and at Day 28, Months 2, 3, 6 and 12.

h Biopsies will be collected from subjects in Cohort 1 and processed by the central laboratory.

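### The SAP 3.7.2 closure table runs each period forward from the nominal day, so no reading of its rows gives closure at the stated visit

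*SAP*

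**What the plan says.** SAP 3.7.2 (Secondary Endpoint Analysis) ties the incidence of confirmed complete closure to a table of periods: "The incidence will be calculated at the time point and covered the time period (table below". The first row covers "Day 14 to <day 21" and the second "Day 21 to <day 28". The later rows follow the same pattern, and nothing comes before Day 14. Denominators are set by visit, for example "Subjects with Day 14 assessment". No p-value is planned.

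The Schedule of Activities, in Protocol Section 2 and repeated in SAP 2.1, allows visits on both sides of the nominal day: Day 14 and Day 21 ± 2 days, Day 28 ± 3, Day 42 and Month 2 ± 4, Month 3 ± 7. Footnote f in the protocol has the blinded assessor looking at the sites "beginning at Day 7 then and daily, or as often as possible, during dressing changes until complete closure is observed". Protocol 9.1.1 dates the event: "Complete wound closure will be considered to have occurred at the earlier of the two observations of complete skin re-epithelialization without drainage".

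SAP 3.1.2 fixes Day 1 as baseline but gives no rule for assigning visits to time points. SAP 5 leaves variable specifications to a separate document.

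**The concern.** A numerator built from forward-running periods and a denominator built from visit labels need not refer to the same moment. Visits are allowed before the nominal day, assessment starts a week before the first row, and closure may be found at dressing changes between visits. The figure labelled Day 14, Day 21 or Day 28 may therefore not be the proportion closed at that visit.

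These time points bear on whether the more widely meshed SOMA site closes as quickly as control. SAP 2.5 reports that in the first 10 subjects both sites were closed by Month 2 without additional autografting. The Month 2 comparison was therefore at its ceiling in those subjects, and the earlier time points are where a difference could still show.

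Early closure is at least conceivable. For the overlay study cited in Protocol 5.5, "the median number of days to >75% closure of the interstices was 8 days compared to 13 days for the control sites". That is partial closure of the interstices, with another product and the same mesh ratio in both arms, so it supports plausibility and no more.

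**Working it through.** The plan gives no figure to reproduce here. The check has three steps.

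**1. Permitted visit days before the row start.** A window of ± w days holds 2w + 1 days, of which w precede the nominal day, so the share is w / (2w + 1). Windows are from the Schedule of Activities and row starts from SAP 3.7.2. The last column reads the rows as study-day intervals.

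| Time point | Window | Days before row start | Share | Row they fall in |
|---|---|---|---|---|
| Day 14 | Days 12-16 | 2 of 5 | 40% | none |
| Day 21 | Days 19-23 | 2 of 5 | 40% | Day 14 |
| Day 28 | Days 25-31 | 3 of 7 | 43% | Day 21 |
| Day 42 | Days 38-46 | 4 of 9 | 44% | Day 28 |
| Month 2 | ± 4 days | 4 of 9 | 44% | Day 42 |
| Month 3 | ± 7 days | 7 of 15 | 47% | Month 2 |

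The documents give no day number for Month 2 or Month 3. Taking Month 2 as Day 56, 60 or 61 and Month 3 as Day 84, 90 or 91 gives the same counts, and the windows do not overlap in any of these cases.

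**2. Three illustrative sites under each reading.** These are constructed examples, not trial data.
- Site 1 is first seen closed at a dressing change on Day 10.
- Site 2 is open at a Day 14 visit held on Day 14 and first seen closed at a dressing change on Day 18.
- Site 3 is open at the Day 21 visit and first seen closed at a Day 28 visit held on Day 26.

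All three are later confirmed, so each is dated to its first observation.

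| Reading | Site 1 | Site 2 | Site 3 |
|---|---|---|---|
| First closure, study-day intervals | no row | Day 14 | Day 21 |
| First closure, visit labels | no row | Day 14 | Day 28 |
| Cumulative or closed status to the end of the period | Day 14 on | Day 14 on | Day 21 on (study days) or Day 28 on (visit labels) |
| Closed at the actual visit | Day 14 on | Day 21 on | Day 28 on |

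Each of the first three lines disagrees with the last for at least one site. On the cumulative reading by study day, the Day 14 figure takes closures up to Day 20 and the Day 28 figure up to Day 41. On either first-closure reading a site enters one row only. A site first closed before Month 2 then adds nothing to the Month 2 row, although it counts as closed for the co-primary endpoint under SAP 2.2.1.

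**3. Size of one site.** SAP 2.1 reports 13 subjects randomized, all in Cohort 1. One site per treatment is 1/13 = 7.7 percentage points if all 13 have the visit, and more if fewer do. The documents do not give visit or closure dates, so the number of sites affected could be anything from 0 to 13 per treatment.

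**The case against.** The rows can be read more kindly. Month 2, Month 6 and end of study have no day numbers, and the denominators are visit labels, so the periods may run from visit to visit. The misplacement of early visits then disappears. If closure is taken as a status, early closures are counted. Both points stand, and they rule out a stronger claim that a reader might infer: that the table necessarily discards the fastest-healing sites. That follows only if rows count first closures. What the kinder readings do not remove is the missing row before the Day 14 visit (visit labels, first closures) or the crediting of later closures to Day 14 (cumulative or status). Only ignoring the period column altogether gives closure at the visit.

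Other limits also stand. Both sites share the subject's visits, so where both are first seen closed at the same early visit they shift together and the paired difference is unchanged. Speed of closure is partly covered elsewhere: the Kaplan-Meier analysis in SAP 3.7.3.2 uses actual dates, and percent re-epithelialization is summarized at the same time points with closed sites set to 100%. The Kaplan-Meier plan names only a median, however, and SAP 6 says figures will not be provided, so it does not replace incidence by visit.

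The separate programming specification may contain a mapping rule. It is not among the documents, and the SAP text that it would implement points the wrong way.

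**Conclusion.** The point holds for one descriptive secondary table. As written, SAP 3.7.2 does not yield confirmed closure at the stated time points on any reading that uses its periods, and it does not say which reading applies. The direction of the error depends on the reading: closures missing, placed one time point early, or added to a visit at which the site was still open.

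The 40-47% range describes permitted calendar days. A reader might take it as the share of visits or closures misplaced; the documents give no dates to support that. Nor do they show a bias between SOMA and control. The second co-primary endpoint is unaffected, since SAP 2.2.1 has its own rule. The 7.7-point step assumes all 13 subjects are in the denominator. The change is worth making, but no primary conclusion depends on it.

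**What to change.** Replace the forward periods with a cumulative rule. At each scheduled visit, count a site as closed if its first confirmed-closure date is on or before the actual date of that visit. The denominator is the subjects who have that visit. Assign visits by the protocol windows: Days 12-16, 19-23, 25-31 and 38-46, Month 2 ± 4 days and Month 3 ± 7 days, with a day number stated for Months 2 and 3. Closures first seen on Days 7-13 then count from the Day 14 visit on, and numerator and denominator refer to the same visit. The Month 6 row should be dropped or explained, because the endpoint stops at Month 3.

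The cost is a short change to the SAP wording and one programming specification. No new data are needed.

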10.3.2. Efficacy Analyses

Efficacy analyses will be performed comparing the differences between treatments within subjects, where appropriate. Descriptive summaries will be reported by treatment site, mesh ratio on SOMA Tx site, cohort and overall.

For calculated percent reduction of donor skin (as defined by $[1-(AG\ Tx\ mesh\ ratio/SOMA\ Tx\ mesh\ ratio) \times 100]$) at Month 2, the log-transformation of the endpoint will be performed, and geometric mean ratio percent reduction of donor skin between treatment site will be presented.

In addition, the areas of treatment and donor sites will be summarized.

A mixed-effect model repeated measures method with covariates, including subject, treatment site, mesh ratio on SOMA Tx site, and cohort will be used for this log-transformed primary endpoint.

Analysis methods will be performed on the FSA, per-protocol set, and also on all observed data.

The summary statistics with 95% confidence interval, standard deviation, Least-squares means and the corresponding standard error will be presented for treatment site, mesh ratio, cohort and overall.

If the mixed-effect model repeated measures model does not converge or violates the model assumptions, the paired t-test will be used. If parametric statistics models are not appropriate, the Wilcoxon signed-rank test will be performed.

Graphs of Least-squares mean \pm standard error and mean \pm standard deviation by visit will be provided.

The same analysis method will be used for secondary efficacy continuous variables on FSA.

For the paired binary endpoint of difference in percent of SOMA Tx sites and AG Tx sites with complete wound closure without additional autografting at Month 2, 95% confidence intervals (CIs) of difference are derived by fitting a repeated measures model with PROC GENMOD that adjusts for the correlation with pairs, and then the 95% CI of difference can be estimated using the Margins Macro, provided by SAS. The P-value will be derived from McNemar's test, if applicable.

The descriptive statistics will also be performed by treatment site, mesh ratio on SOMA Tx site, cohort and overall and on FSA, per-protocol set, and all observed data. The missing binary data will be imputed as non-responders.

For other paired secondary efficacy binary endpoints, the same analysis as above will be used on FSA.

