Following excision, a total of 20 subjects (Cohort 1) will be randomized into one of 2 groups, Group 1 and Group 2.

Following completion of the Day 28 assessments, each subject will be determined to be a success or failure based upon the criteria below:

- % closed at Day 28, with success declared if the difference between paired wounds
 10%, and
- Total score of Observer assessment of the POSAS at Day 28, with success declared if the difference between paired wounds < 20%.

Group success will be declared if \geq 80% subjects are determined to have treatment success within that group. Only one of the 2 SOMA Txs, m+1 or m+2, will be determined to meet the *a priori* established criteria above and become the SOMA Tx in Cohort 2.

Treatment Groups and Duration:

This study is open-label. Subjects will serve as their own control. Subjects will be randomized to receive autograft, meshed at a ratio per clinician judgment at 1 treatment site (m), and StrataGraft overlay of autograft at either m+1 (i.e., group 1) or m+2 (group 2), relative to the control autograft mesh ratio.

It is anticipated that each subject will participate in this study for up to 14 months: up to 2 weeks of screening followed by up to 12 months (± 4 weeks) of post-treatment observation.

Estimated Duration of Study

Enrollment ~36 months.

Duration of subject participation up to 60 weeks.

Total study duration ~96 months.

Study Was Terminated Early by Sponsor

Study enrollment was terminated on 12 January 2024 due to a decision to voluntarily discontinue sale and manufacture of StrataGraft for business reasons. A total of 13 subjects were randomized, all in Cohort 1, at the time of termination of enrollment. Follow up for enrolled subjects was completed in April 2024.

Scientific Rationale for Study Design

The current standard of care for closure of FT burns is autografting, i.e., the surgical harvest of healthy skin from an uninjured site and subsequent transplantation of the donor tissue to the wound following surgical excision of nonviable tissue from the burn. While this method is effective in achieving closure of the original wound, optimal sites for the harvest of donor skin are often limited, and closure of large areas of injury may necessitate sequential re-harvest of available donor sites. Additionally, the donor site is painful, susceptible to infection and scarring,

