2.5 Ad-hoc Data Review

Due to slow enrollment, the sponsor performed a preliminary assessment of the efficacy and safety of the product in April 2023 to determine the appropriateness of amending the ongoing Phase 1/2a StrataSOMA clinical study to a seamless Phase 1/2/3 study design. To this end, the sponsor performed an ad-hoc data analysis for the first 10 subjects enrolled in Cohort 1 after 1st 10 subjects completed primary endpoints assessments. Results of this data review were included

in Sponsor Meeting Materials for a Type B meeting with FDA to discuss the proposed clinical study amendment.

The ad-hoc data review demonstrated that all of the first 10 subjects enrolled in the StrataSOMA study achieved confirmed complete wound closure by or before Month 2 without additional autografting on both SOMA and AG treatment sites, regardless of whether they were randomized to the m+1 or m+2 group (i.e., 100% of the SOMA treatment sites achieved confirmed complete wound closure by or before Month 2 without additional autografting).

Additionally, SOMA treatment decreased the amount of donor tissue required to close treated sites relative to the control AG treatment site by 35% and 57% for autograft mesh ratios m+1 and m+2, respectively, without sacrificing cosmetic outcomes, as evidenced by comparable POSAS scores at Months 2 and 3.

For safety, ad hoc analyses of TEAEs or SAEs for the first 10 patients through the data cutoff showed that most TEAEs and SAEs were typical of what is observed in burn wounds and during wound healing. The safety profile at the StrataGraft treatment sites was similar to that of the control treatment sites, and no new safety signals were identified.

For details of the ad-hoc analyses, see the Type B Meeting Briefing Materials submitted in IND 010113 Sequence 0151 on 27 November 2023 (see References).

This ad-hoc data analysis will not alter the screened significance level of the entire study.

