3 STATISTICAL METHODS AND CONVENTIONS

3.1 General Conventions

- Unless otherwise noted, the number of subjects (n), mean, standard deviation, median, minimum, and maximum will be presented for continuous variables and frequency and percentage of subjects in each category will be presented for discrete variables.
- Unless otherwise noted, confidence intervals (CIs) will be 2-sided 95% CIs.
- Listings will be sorted by subject identification.
- Statistical analyses will be done using Statistical Analysis Software (SAS®) version 9.3 or higher.
- All statistical tests will be two-sided with a final significance level of 0.05, unless stated otherwise.

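### For scar score, re-epithelialization and durable closure, the SAP omits the paired SOMA minus AG difference and its interval, and does not list this departure from the protocol

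*SAP*

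**What the plan says.** SAP 3.7.2 treats the secondary endpoints as follows.

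- **POSAS/PSAQ:** n, mean, median, SD, minimum and maximum for each site at each visit. For the POSAS total, "The screened P-values on total score of POSAS between treatment sites is derived from paired ttest". PSAQ gets descriptives only.
- **Percent re-epithelialization:** the same descriptives per site, and a screened p-value from a paired t-test. A closed wound counts as 100%.
- **Durable closure (Months 6 and 12):** "The proportion and 95% CI will be calculated using the exact method to the binomial distribution". No between-site comparison is named.
- **Incidence of confirmed closure:** the SAP says that no p-value will be given for the difference between sites.

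Protocol 10.3.2 planned more. For the first co-primary endpoint, "The summary statistics with 95% confidence interval, standard deviation, Least-squares means and the corresponding standard error will be presented" by treatment site, mesh ratio, cohort and overall, and the same method was to serve the secondary continuous variables. For the second co-primary it specified a 95% interval for the paired difference, and then: "For other paired secondary efficacy binary endpoints, the same analysis as above will be used on FSA".

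SAP 2.2.7 sets out the changes from the protocol's statistical section. On analysis methods it records a change for the first co-primary endpoint only.

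SAP 2.5, on the ad-hoc review of the first 10 subjects, says that donor tissue was reduced "without sacrificing cosmetic outcomes, as evidenced by comparable POSAS scores at Months 2 and 3".

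**The concern.** A wider mesh lowers the calculated donor-skin requirement almost by construction, because that endpoint is a ratio of mesh ratios. What the trial can inform is whether the saving comes with a worse wound or scar. That calls for an estimate of the SOMA minus AG difference and a statement of how large a deficit the data leave open. A test of no difference supplies neither.

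The design is paired, and the plan does not use the pairing for estimation in these three endpoints. Per-site SDs do not give the SD of the within-subject difference, which also depends on the correlation between the two sites. Separate proportions for durable closure do not give the paired difference its interval, which depends on how many subjects are discordant.

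With so few subjects, a reader who sees only a non-significant p-value may take it as support for comparability. SAP 2.5 already applies that word to POSAS, with no interval or criterion beside it.

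**Working it through.** The plan has no figure to reproduce: Protocol 10.1 and SAP 2.3 both say that no sample size calculation was done.

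**Inputs**

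- Test level, SAP 3.1: "All statistical tests will be two-sided with a final significance level of 0.05, unless stated otherwise".
- Number of pairs, SAP 2.1: "A total of 13 subjects were randomized, all in Cohort 1, at the time of termination of enrollment". This is a ceiling. SAP 3.1.1 uses observed values without imputation for these endpoints. Enrollment stopped on 12 January 2024 and "Follow up for enrolled subjects was completed in April 2024", so later visits may have fewer pairs.
- SD of the paired differences (SDd): not given. Assumed range 10 to 40 percentage points.
- Reference sizes of 10 points (re-epithelialization) and 20 points (Observer POSAS total): taken from the Day 28 advancement criteria in Protocol 10.3.1, which classify individual subjects. They are read here as percentage points and used only to give a scale.

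**Step 1: precision.** Half-width of the 95% t interval = t(0.975, n−1) × SDd / √n. At n = 13 this is 2.179 / 3.606 = 0.604 SDd.

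**Step 2: detectable difference.** The power of the two-sided paired t-test comes from the noncentral t distribution with n−1 degrees of freedom and noncentrality (δ/SDd)√n. Solving for 80% power:

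| Pairs | Half-width (SDd) | True difference for 80% power (SDd) |
|---|---|---|
| 13 | 0.604 | 0.847 |
| 10 | 0.715 | 0.996 |
| 7 | 0.925 | 1.273 |
| 6 | 1.049 | 1.435 |

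The rows for 7 and 6 illustrate a near-even split of the 13 between m+1 and m+2. The documents do not give the actual split.

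**Step 3: chance of non-significance when a true deficit exists, n = 13.** This is 1 − power. For a 10-point deficit and SDd = 15, the noncentrality is (10/15) × 3.606 = 2.404 and the result is 0.40. Over the range:

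| Assumed SDd (points) | Half-width (points) | True deficit 10 points | True deficit 20 points |
|---|---|---|---|
| 10 | 6.0 | 0.09 | <0.01 |
| 15 | 9.1 | 0.40 | <0.01 |
| 20 | 12.1 | 0.62 | 0.09 |
| 25 | 15.1 | 0.74 | 0.25 |
| 30 | 18.1 | 0.80 | 0.40 |
| 40 | 24.2 | 0.87 | 0.62 |

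A non-significant p-value is therefore weak evidence against a 10-point deficit unless SDd is near 10. Against a 20-point deficit it is informative up to an SDd of about 20 and weakens beyond that. The reader can tell which case applies only if SDd or the interval is reported.

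**Step 4: the texts side by side.** Protocol 10.3.2 carries intervals over to the secondary continuous and paired binary endpoints. SAP 3.7.2 specifies none for POSAS or re-epithelialization, and only an interval for a proportion for durable closure. SAP 3.7 speaks generally of within-subject differences where appropriate but names no statistic. SAP 3.1 fixes the level of intervals without requiring any. SAP 3.7.1 keeps a paired-difference interval for the second co-primary endpoint, so such reporting is feasible in this trial.

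**The case against.** Much can be said for the plan, and several stronger readings fail.

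- A reader might infer that the SAP decides by p-value whether SOMA matches autograft. It does not. SAP 3.7.1 calls all p-values in the tables screened p-values for signal exploration, SAP 3.7.2 repeats the label, and no rule equates non-significance with comparability. SAP 2.5 does not tie its word to a p-value; its details lie in a briefing document outside this review.
- A reader might extend the p-value criticism to closure in general. Co-primary closure has a paired-difference interval, closure incidence gets no p-value, and durable closure has an interval without a test. For durable closure the gap is the missing paired interval.
- A reader might say that a relevant deficit would usually be missed. That depends on an SD the documents do not give. For a 20-point difference, the chance of non-significance stays below one half up to an assumed SD of 30.
- The protocol did not expressly promise a paired-difference interval for the continuous endpoints, and the paired t-test is its own named fallback. This stands. The dropped items are the planned 95% intervals and least-squares means; the explicit paired-difference interval was for the binary endpoints.
- With complete pairs, a determined reader could recover the difference from the two means, and the SD from the p-value. This also stands in part. It fails when pairs are incomplete or when the difference or p-value is rounded near its limit, and it is no substitute for printing the interval.
- The practical stakes are low. Enrollment ended at 13 subjects, Cohort 2 never opened, manufacture was discontinued, and the documents describe no later study to size. This stands and limits the weight of the point.

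**Conclusion.** The point holds as a reporting gap. For POSAS total and percent re-epithelialization, the only between-site statistic is a screened difference-test p-value; for durable closure there is no paired comparison. The protocol planned intervals for these endpoints and SAP 2.2.7 does not list their removal.

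The precision figures rest on 13 complete pairs and a paired t model; fewer pairs make them worse. The probabilities of non-significance also rest on the assumed SDs.

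The 10% and 20% limits cannot be read as group-level margins. They are per-subject criteria at Day 28 that feed an 80% advancement rule, the 20% limit covers only the Observer total, and neither applies to durable closure or to later visits. Nor do the documents support treating this as a fault that must be cured before the analysis can stand: the trial is terminated and exploratory, and the improvement is modest.

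**What to change.** In SAP 3.7.2 and the table shells:

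- For POSAS total and percent re-epithelialization at each visit, report the number of pairs, the within-subject SOMA minus AG difference, its SD and a two-sided 95% interval. Where both wounds are closed in most subjects, most re-epithelialization differences will be zero and a t interval will say little; use a median difference or a distribution-free interval there.
- For durable closure at Months 6 and 12, report the paired difference in proportions with an exact or score 95% interval for paired data.
- Give these overall and, descriptively, by m+1 and m+2.
- State that a non-significant screened p-value is not evidence of comparability. If the 10% and 20% figures are quoted, label them as reference sizes at Day 28 (20% for the Observer total only), not as margins.
- List the departure from Protocol 10.3.2 in SAP 2.2.7.

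The cost is some SAP wording and a few table columns, with no new data. The intervals will be wide, especially within mesh groups.
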